Colonoscopy complications	Monthly review of all colonoscopies associated with program procedures, and any complications within 30 days of procedure completion, including, but not limited to: bleeding, perforation, myocardial infarction, death.
Any unanticipated serious or non serious adverse event	Monthly review with all program staff Passive reporting by the clinical lab, endoscopy lab, JPS physicians, or any program participants to program staff.

Plans for medical or professional intervention in the event of adverse effects

- 1. Procedure for responding to loss of confidentiality. The study participant who experiences loss of confidentiality will be informed by one of the study primary investigators in writing and by phone of the loss of confidentiality. The IRB will be informed in case of this event.
- 2. Procedure for responding to physical harm from colonoscopy. The study participant will immediately be informed of the physical harm, and appropriate medical and surgical interventions will be facilitated. The IRB will be informed in case of this event.
- 3. Procedure for responding to psychological harm from screening. The study participant who experiences psychological harm will be informed by one of the study primary investigators in case of this event. Appropriate referrals for medical and/or psychological care will be facilitated. The IRB will be informed in case of this event.

The protocol will be stopped for any of the following reasons:

- Unanticipated serious adverse event such as loss of confidentiality
- Unanticipated death resulting from any study activity
- Request of either Institutional Review Board
- Unanticipated event deemed appropriate indication for stopping the trial by the PI

Plans for assuring data accuracy, data security, and protocol compliance include:

- Access to study data only by designated study personnel
- Study data will be kept in a locked room, on a password protected computer, with password protected file. All paper case-report forms will be destroyed after data entry, and kept in a locked room within a locked filing cabinet until data entry and subsequent destruction
- Daily backup of study data to a central, firewalled, password protected server at Moncrief Cancer Institute, University of Texas Southwestern Medical Center
- Daily monitoring of protocol compliance through conversations between the principle investigator and research assistants

The mechanisms for reporting unanticipated problems will include:

• Report of the unanticipated problem to the Institutional Review Boards at University of Texas Southwestern Medical Center and John Peter Smith Hospital Health System immediately (within 1 business day).

Continuing Review will be performed by the IRB on an annual basis, or more frequently, if required. As part of the Continuing Review submission to the IRB:

- On the IRB Form for continuing review, items referencing unexpected and serious adverse events will be completed appropriately with a comment to describe the event(s) according to IRB template instructions.
- The Progress Report will be completed according to IRB template instructions and include the principal investigator's a summary of unexpected and serious adverse events and protocol deviations with an analysis of the safety profile of the research.
- If not already done, protocol documents (e.g. protocol, project summary) that require changes based on changes to the risk profile of the research will be submitted as a Modification with the Continuing Review according to IRB instructions.
- A declaration of on-going operational feasibility. If the enrollment rate in the previous year is not sufficient to reasonably reach planned enrollment, a plan will be offered to assure completion of the study.

ClinicalTrials.gov

The trial will be registered in ClinicalTrials.gov prior to being started.

Procedures to Maintain Confidentiality:

Plans for assuring data accuracy, data security, and protocol compliance include:

- Access to study data only by designated study personnel
- Study data will be kept in a locked room, on a password protected computer, with password protected file. All paper case-report forms will be destroyed after data entry, and kept in a locked room within a locked filing cabinet until data entry and subsequent destruction
- Regular backup of study data to a central, firewalled, password protected server at Moncrief Cancer Institute, University of Texas Southwestern Medical Center
- Daily monitoring of protocol compliance through conversations between the principle investigator and research assistants
- Database and patient records accessed by research staff from JPS Network computers, connected by VPN to UT Southwestern Medical Center, and Moncrief Cancer Institute

Potential Benefits:

Individuals in the age range from 50 to 64 are most likely to benefit from CRC screening²³. Modeling studies suggest that a life expectancy of at least 8 years is required for a given patient to realize the benefits of screening over non-screening¹³. In fact, one group has suggested that Medicare consider supporting screening for those under 65, as this could prevent CRC associated morbidity and mortality when individuals acquire age of Medicare eligibility²⁴.

Biostatistics: EVALUATION STRATEGY

Overview. Our overarching evaluation goal is to rigorously evaluate program outcomes. The evaluation will be strengthened by our prior experience and systematic approach to evaluating program outcomes. Our evaluation strategy has been designed to provide the most interpretable results possible, and position local and state public health officials to assess program impact and areas for improvement. The evaluation will be lead by [name], a biostatistician, [name], an epidemiologist, and [name], a physician and clinical researcher. We have a track record of completing sophisticated program evaluations, and have worked together on prior analyses. We have developed several primary evaluation aims, as well as a number of secondary evaluation aims. It should be noted that all CPRIT required program evaluations are addressed.

Consistent with Goal 3, for our primary evaluation aims, we will:

Evaluation Aim A) Determine screening rate improvement after expanding screening outreach to all unscreened patients. We predict the population screening rate will be $\geq 10\%$ higher after outreach expansion compared to baseline.

Evaluation Aim B) Compare rates of initial and repeat screening completion among 1) Patients offered a modest financial incentive to complete screening, in addition to outreach invitations, vs. 2) Patients offered outreach invitations alone.

Evaluation Aim C) Among patients receiving financial incentives to complete screening, compare rates of initial and repeat screening completion between patients receiving \$5 vs. \$10 incentives.

Evaluation Aim D) Assess all CPRIT required outcomes, including increase in early stage cancer detection from baseline, as well as health system changes required to boost screening.

Approach to Evaluation Aims

Evaluation Aim A) Determine screening rate improvement after expanding screening outreach to all unscreened patients. The denominator population for evaluating baseline and end of Year 3 screening rates will consist of patients meeting the following criteria: 1) Age 50-64, 2) Uninsured, but participants in JPS's medical assistance program for the uninsured, 3) One or more visits to a JPS primary care clinic within a year, 4) Address and phone number on file, 5) No history of CRC or colon resection, 6) Not incarcerated

Thus, the denominator population for our baseline and end of Year 3 follow comparisons of screening rates generally includes patients age-eligible for screening outreach. The numerator for calculation of screening rates will be the number of patients who are up-to-date with screening based on colonoscopy within 10 years, sigmoidoscopy within 5 years, or stool blood test (guaiac FOBT or FIT) within the last year, measured by HEDIS criteria. Thus, the screening rate at baseline and at end of Year 3 will be defined by:

Screeni ng Rate ▪ _	# up-to-date with
	screening

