Overall, because our outreach program already includes all outreach intervention components recommended by the Task Force on Community Preventive Services, and because financial incentives show promise for changing health behaviors that are far more complex than completing FIT screening, we need to determine whether financial incentives boost CRC screening over and above our organized outreach program. Our proposed prevention program will determine whether offering financial incentives, in the form of either a \$5 or \$10 gift card in exchange for screening completion, are an effective adjunct to our organized outreach approach.

BACKGROUND SUMMARY. CRC is an important public health problem, particularly for the uninsured, who have the lowest screening rates and worst CRC outcomes. Our prior, CPRIT sponsored Evidence based Prevention program focused on the uninsured was successful in boosting

screening participation by 29%. Organized outreach was twice as effective when patients were offered FIT vs. colonoscopy screening (33% vs 14%). Our program was highly evidence based and successful, but several challenges remain. We must expand our organized outreach to all individuals eligible for screening. Program sustainability must be ensured by transferring primary responsibility for screening promotion delivery to JPS. We must determine if participation rates remain high when screening is offered annually because effective, evidence based FIT screening requires annual test completion. Finally, innovation is required. Offering modest financial incentives to complete screening, beyond offering free tests, may be a particularly effective adjunct to our current outreach approach. The specific aims and outreach approach outlined below have been carefully crafted to leverage the screening needs of the uninsured, our prior experience with a successful outreach program, and innovative ideas for screening to improve CRC screening to deliver screening and advance evidence based screening practice.

Concise Summary of Project:

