Follow up of patients with a CRC will consist of navigation to first treatment consultation visit. We will arrange for a surgery or oncology clinic follow up for all patients with a CRC diagnosis if such follow up is not already scheduled by the colonoscopist who diagnosed the CRC. These calls will be made daily for up to one week. The goal will be to have a first treatment consultation visit within 2 weeks of CRC diagnosis. Patients will be reminded of these visits 5 days and 1 day prior to the scheduled appointment. *All results/recommendations will also be sent to the patient via mail, and to the patient's primary provider within 1 week of the result.*

Financial incentives.

A group of 2,000 individuals will be randomly assigned to receive a modest financial incentive to complete screening, in addition to the organized outreach program. The incentive will be sent in exchange for screening completion. Incentives will be sent to a subset of patients, rather than all patients included in the screening outreach program for two main reasons. First, it is unknown whether offering financial incentives results in meaningful increases in screening participation. By selecting a subset, rather than all patients to receive financial incentives, we will be able to determine if offering financial incentives, in addition to the current program, is more effective for promoting screening than outreach invitations alone. Evaluating impact of incentives as an adjunct to organized screening outreach for promoting CRC screening will address the lack of evidence on impact of incentives highlighted by the Task Force on Community Preventive Services²⁰. Second, budget constraints preclude offering incentives to all patients. To randomly assign the 2,000 individuals who will receive the financial incentive, we will use SAS procedures. The rationale for choosing 2,000 individuals to receive incentives is discussed in below. To determine whether offering a \$10 vs. \$5 incentive results in substantially

higher screening completion, 1,000 patients will receive an incentive for \$5, and 1,000 patients will receive the \$10 incentive offer.

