The incentive will consist of either a \$5 or \$10 gift card to a local retailer that will be sent to the patient upon return of an FIT kit. Incentives will be mailed by the JPS outreach team, in exchange for successful FIT completion, after the FIT has been returned. \$5 and \$10 incentives were chosen for several reasons. First, these levels of incentives, if shown effective, could be potentially sustained by the JPS system beyond the timeframe of the grant. Higher incentives, while potentially more powerful in inducing participation, would be unsustainable and therefore do not merit study at this time. Comparing \$5 and \$10 incentives is important because if offering incentives is effective in boosting screening, it is important to know the minimum incentive required for meaningful changes in participation. Incentives are to be offered to all patients who are assigned to the incentive strategy. We considered, but rejected, restricting incentives to only patients who initially do not respond to screening invitations. This was because restricting incentives to non-responders would logistically complicate outreach activities. It is important to note that patients meeting study inclusion criteria must have a minimum of 1 visit to a JPS Primary Care clinic within the last year. Considering these patients have an established baseline relationship with the JPS primary care system, the addition of a modest financial incentive should not create undue influence in patients that otherwise would still have exposure to information on the benefit of screening. Since participation in this standard of care screening poses minimal to no risk, the chances that incentives may motivate research participants to take unnecessary risks are low.

Screening Completion Follow Up. Follow up for determining screening completion for all included patients will be through the end of Year 3 regardless of whether or not patients respond to screening invitations. As is explained below, screening rates will be measured for all patients included for outreach invitations. For patients who die on follow up or who do not have additional health system encounters, follow up will be censored at time of death or last health encounter, respectively.

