we will even have 90% power to detect a smaller screening rate increase of \geq 5% (Power was computed with nQuery Advisor Software v.7.0).

Evaluation Aim B) Compare rates of initial and repeat screening completion among 1) Patients offered a modest financial incentive to complete screening, in addition to outreach invitations (n=2,000), vs. 2) Patients offered outreach invitations alone (n=~18,000). The rate of initial screening completion will be defined by:

Initial	# patients completing a FIT
Screening	Year 1
Completion Rate =	# of patients sent FIT invitation Year 1

We will compare the initial screening completion rate for patients offered the financial incentive, in addition to screening outreach, to the initial rate for patients offered screening outreach alone using a Chi-square test of proportions, with a 2-sided p value <0.05

considered statistically significant. The rate of repeat screening for Years 2 and 3 will be defined by:

Year 2	# patients completing FIT	Year 3 Repeat	# patients completing FIT
Repeat	screening Year 2	Completion	screening Year 3
Completion	# patients completing FIT Year 1	Rate =	# patients completing FIT Year 2
Rate =	with normal result		with normal result

We will compare initial FIT completion rates for the financial incentive plus organized outreach vs. organized outreach alone groups using a Chi-square test, with a 2-sided p value <0.05 considered statistically significant. The same approach will be taken for comparing repeat FIT completion rates for Years 2 and 3.

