Sample size for Evaluation Aim B. The sample size for this aim will be 2,000 for the financial incentive group plus outreach group, and at least 18,000 for the outreach group alone. The sample size for the financial incentive group was chosen based on sample size required for sufficient power to detect expected differences between offers of \$5 and \$10 gift card incentives outlined in Aim C below. The sample size for the outreach group alone was based on including all patients included in the screening outreach program who will not receive financial incentives. With 2,000 patients assigned to the financial incentive plus outreach group, and 18,000 patients assigned to the outreach alone group, we estimate over 90% power to detect differences in initial screening participation of 5% or more at a 5% two-sided significance level. Thus, we will have more than enough power to detect clinically meaningful differences of 10% or more in initial FIT completion. Because of the lack of prior data on repeat FIT participation rates, and under the sample size discussion for Evaluation Aim A above, we do not present formal power calculations for comparisons of repeat FIT completion rates, but expect that we will be able to make meaningful comparisons based on the large number of patients included for evaluation.

Evaluation Aim C) Compare rates of initial and repeat screening among patients receiving \$5 vs. \$10 financial incentives in addition to outreach invitations. For this comparison, we will use the same definitions outlined under "Evaluation Aim B" above for the initial screening completion rate, and the Year 2 and 3 repeat completion rates. For these outcomes, we will compare the outcome rate for patients receiving the \$5 vs. \$10 incentive, using a Chi-square test of proportions, with a 2-sided p value <0.05 considered statistically significant.

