Sample size for Evaluation Aim C. The sample size for Evaluation Aim C is based on comparing the initial screening participation rate between the \$5 vs. the \$10 incentive groups. As is outlined in Section A.3, previous data suggest that financial incentives are effective for promoting complex healthy behaviors such as quitting smoking³⁹⁻⁴¹. Further, we believe that incremental (modest) incentives are likely to significantly increase screening completion. First, we assumed that a 10% or more difference in initial screening participation would be clinically meaningful. Second, we assumed that the screening completion rate associated with the \$5 group would be 43%, and that the rate for the \$10 group would be at least 53%. The 43% rate was chosen because our response to FIT invitations with our prior outreach program was 33%, and we would consider a 10% or more increase Version 8, June 29, 2015

in screening completion associated with the \$5 intervention over organized outreach alone to be clinically meaningful. Similarly, the 53% rate was chosen for the \$10 group because we would consider a 10% or more increase in screening completion associated with the \$10, rather than the \$5 group to be clinically meaningful. Under these assumptions, with an alpha=0.05, we estimated 1090 patients (n=545 in the \$5 group and n=545 in the \$10 group) would be required for 90% power to detect a statistically significant difference of 10% or more in initial screening participation. Because we recognize uncertainty in the estimating the expected difference between the two groups, and because we wanted to increase our ability to conduct exploratory comparisons of repeat FIT participation rates associated with the \$5 and \$10 groups, we increased the planned sample receiving financial incentives to 2,000 (n=1,000 in the \$5 group and n=1,000 in the \$10 group). Thus, we will have more than enough power to detect differences of 10% or more in initial screening participation.

Evaluation Aim D) Assess all CPRIT required outcomes, including increase in early stage cancer detection from baseline, as well as systems changes required to boost screening. To assess increase in early stage cancer detection from baseline, we will compute proportion of CRC patients with early stage cancer at baseline and at end of Year 3. JPS Cancer Registry data will be used for this computation. Rate of early stage cancer will be defined as:

Early Stage	# CRC patients with SEER Summary

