Secondary analyses. We plan to conduct several secondary analyses. First, we recognize that results from Evaluation Aim A, in which baseline screening rates will be compared to follow up screening rates at year 3, could be confounded by time trends in CRC screening rates, which generally have been increasing over time. Accordingly, we will compare the observed rate of CRC screening in Year 3 to the expected rate of CRC screening based on time trends in screening at JPS. The expected rate will be estimated using the secular trend for CRC screening using annual screening rates for each of the 7 years 2006-2011 prior to start of our prevention program in 2012. All rates will be standardized by gender and age strata (50-54, 55-59, and 60-64 years) to the population distribution of men/women and these age strata for 2012, and a standardized incidence ratio (SIR) will be computed. An SIR greater than 1, with an associated 95% confidence interval that does not cross 1 will be interpreted as evidence to support impact of our outreach intervention beyond time trends in CRC screening rates. We have previously used this approach to assess impact of a University of Texas health plan policy that waived copays for colonoscopy screening on CRC screening rates which began in 2009, in which we compared colonoscopy uptake 2002-2008 to uptake after policy institution⁴⁶.

Version 8, June 29, 2015

Second, to identify factors independently associated with screening outcomes, we will construct several logistic regression models. For example, to identify predictors of initial screening completion, we will create a model using initial screening completion rate as the primary outcome (dependent) variable, and several potential predictors of completion. Predictors considered for model inclusion will include age, sex, race/ethnicity, frequency of primary care visits, exposure to the screening outreach program, and exposure to financial incentives. A similar model will be created with the outcome of programmatic screening as the dependent variable. For these exploratory analyses, 2-sided p values of 0.05 will be considered statistically significant.

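### The plan wants the smallest effective incentive but plans no comparison of $5, or of $10, with outreach alone

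*Combined protocol and SAP*

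**What the plan says.** The Financial incentives section gives two reasons for choosing $5 and $10. The first is that "these levels of incentives, if shown effective, could be potentially sustained by the JPS system beyond the timeframe of the grant". The second is that, if incentives work, "it is important to know the minimum incentive required for meaningful changes in participation". The Background asks whether either amount is worth adding, that is, whether a "gift card in exchange for screening completion, are an effective adjunct to our organized outreach approach". The Financial incentives section also states that "it is unknown whether offering financial incentives results in meaningful increases in screening participation".

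The evaluation strategy plans two incentive comparisons, each a chi-square test at two-sided 0.05:

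- **Aim B** pools the two amounts (n=2,000) against outreach alone (n about 18,000): "We will compare the initial screening completion rate for patients offered the financial incentive, in addition to screening outreach, to the initial rate" with outreach alone.
- **Aim C** compares the amounts with each other: "For these outcomes, we will compare the outcome rate for patients receiving the" $5 or the $10 offer (1,000 each).

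The Aim C sample-size section sets a yardstick for $5 against no incentive. It would regard a gain of 10 points or more from the $5 "intervention over organized outreach alone to be clinically meaningful". That figure serves only to set the assumed $5 rate (33% to 43%); no estimate, interval or test is attached to it. The exploratory logistic model under Secondary analyses lists "exposure to the screening outreach program, and exposure to financial incentives" among its predictors and does not say whether incentive exposure is split by amount.

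**The concern.** The smallest incentive that gives a meaningful change can only be judged against no incentive. Aim B does not separate the amounts, and Aim C has no unincentivised reference. If the health system chooses an amount to sustain from which tests were significant, it may go wrong in two ways. When both aims are significant, $5 may add nothing, part of the meaningful gain or all of it. When Aim B is significant and Aim C is not, $5 may be as good as $10 or may do nothing. A $5-versus-outreach contrast chosen after the results are seen would carry less weight than one written down beforehand.

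**Working it through.** **Inputs.** From the Aim C sample-size section: 33% with outreach alone, 43% with $5, 53% with $10, and a 10-point meaningful difference. From Financial incentives: 1,000 per amount. From Aim B: about 18,000 controls.

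Sub-Study Procedures says that all incentive patients were enrolled in Year 1, so concurrent controls number fewer than 18,000. The documents give no Year 1 count. I assume 8,319 (10,319 not up to date in 2011, minus 2,000) and show the range 4,000 to 18,000.

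**The plan's own figure.** For 43% vs 53%, two-sided 0.05 and 90% power, without continuity correction:

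n = [1.96·√(2·0.48·0.52) + 1.2816·√(0.43·0.57 + 0.53·0.47)]² / 0.10² = 523 per group.

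With the continuity correction, n = 543, which agrees closely with the stated 545. With 1,000 per group, power is 99.4%.

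**What the two differences determine.** Let p0, p5 and p10 be the three completion rates. With equal arms the pooled rate is (p5 + p10)/2. Let B = (p5 + p10)/2 − p0 and C = p10 − p5. Then p5 − p0 = B − C/2.

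- Planned rates (33/43/53): B = 15, C = 10, so the $5 gain is 15 − 5 = 10 points.
- $5 inert (33/33/43): B = 5, C = 10, so the $5 gain is 5 − 5 = 0.

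The estimates therefore fix the $5 effect.

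**What the significance results determine.** Simulated uncorrected chi-square tests, 600,000 trials per case; ranges run over 4,000 to 18,000 controls.

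| True rates, outreach/$5/$10 (%) | $5 gain (points) | Result pattern | Share of trials |
|---|---|---|---|
| 33/33/43 | 0 | B and C both significant | 96.5-99.0% |
| 33/38/48 | 5 | B and C both significant | 99.5% |
| 33/43/53 | 10 | B and C both significant | 99.4% |
| 33/38/38 | 5 | B significant, C not | 92.0-94.3% |
| 33/38/43 | 5 | B significant, C not | about 38% |
| 33/33/38 | 0 | B significant, C not | 17.0-21.5% |

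With a 36% control rate (the return rate quoted in the sub-study rationale), the first case gives 95.9-98.8%, and 36/46/56 gives 99.4-99.5%. Neither pattern of significance separates a useful $5 from a useless one.

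**What a direct contrast gives.** The 95% half-width for $5 minus outreach at 38% vs 33% with 8,319 controls is 1.96·√(0.38·0.62/1000 + 0.33·0.67/8319) = 3.2 points. Over $5 rates of 33% to 43% and 4,000 to 18,000 controls it runs from about 3.0 to 3.4.

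- If the true rates are 33/38/43, the upper limit for $5 lies below 10 in 83-88% of trials.
- If the true $5 gain is exactly 10, the interval contains 10 in 95% of trials.
- If tested at alpha 0.025, power for 33% vs 38% is 77-84%, and for 33% vs 43% it is above 99.9%. The pooled test has 97-99% power when both amounts add 5 points.

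**The case against.** The strongest reply is that the plan follows a two-step logic: show that incentives work (Aim B), then compare the amounts (Aim C). The sentence on the minimum incentive is conditional on incentives being effective, and the same section gives the purpose of the split as learning whether $10 does substantially better than $5. The three rates will be reported, and the identity above recovers the $5 effect. If $5 were inert, its observed difference would centre on zero with a standard deviation of about 1.6 points (8,319 controls); at the planned rate it would centre on 10. A reader of the rates would not confuse the two.

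Much of this stands. A reader might infer that Aims B and C leave the $5 effect unidentifiable, or that the trial cannot answer its question. The documents do not support that: the arms are randomised, equal in size and large enough. What the reply does not supply is a planned estimate with its uncertainty, a reading against the plan's own 10-point yardstick, or a guard against taking a non-significant Aim C as equivalence.

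Two further objections limit the remedy. First, at a true 10-point gain the interval will usually be inconclusive on the threshold, although it will show benefit. Second, testing the added contrasts brings more multiplicity: with Holm applied to those two alone, the chance of at least one false positive across all four incentive tests is about 10.7% under the global null, against 9.8% for Aims B and C alone (8,319 controls).

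**Conclusion.** The gap is real and lies in prespecification, not in design or sample size. The plan states a question about each amount against no incentive and a threshold for judging $5, but neither planned comparison addresses it directly. Significance in both aims is almost equally likely whether $5 adds nothing (about 97-99%) or the planned 10 points (99%), and a non-significant Aim C leaves the adequacy of $5 open. These figures assume 33% completion with outreach alone, 1,000 per amount and 4,000 to 18,000 concurrent controls; a 36% control rate gives the same conclusion. The case of an inert $5 with $10 adding 10 points is illustrative and not one the plan expects.

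It would be too strong to say that the harm is certain or that the answer is lost, because the observed rates would show the difference. The point is worth correcting because the correction is cheap and the result is meant to guide which amount to sustain.

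**What to change.** Keep Aims B and C, and add to the analysis plan:

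1. The differences $5 minus outreach alone and $10 minus outreach alone in initial completion, among concurrently randomised Year 1 invitees, each with a 95% confidence interval.
2. The reading against the 10-point threshold: an upper limit below 10 shows less than the meaningful gain, and an interval containing 10 is inconclusive on that threshold.
3. A statement that a non-significant Aim C does not show that $5 and $10 are equivalent.
4. If the two contrasts are also tested, a multiplicity rule for them (Holm is one option), with a note that it does not control error across Aims B and C.
5. A date. Version 8 (June 2015) describes incentive enrolment as having taken place in Year 1, with the programme nearly two years in. The addition must be made before arm-level results are examined; otherwise the contrasts should be labelled post hoc.

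The cost is two more comparisons and lower power for each amount than for the pooled test (77-84% at alpha 0.025 against 97-99%, for 5 points). No extra patients or data are needed.
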